Weight	•	•	•	•	•	•	•	•	•										
Height	•																		
Laboratory Samples ¹	•	•				•			•										
Physical Examination	•	•	•	•	•	•	•	•	•										
Parkinson's Disease Assessments ²	•	•	•	•	•	•	•	•	•										
Study Treatments Administration		•	•	•	•	•	•												
24 hours Telephone Encounter		•	•	•	•	•	•												
Video Documentation	•	•				•			•										
AE and SAE assessments		•	•	•	•	•	•	•	•										

2. Parkinson's disease Assessments – MDS-UPDRS, VAS pain and muscle spasms, Neuro-Quality of Life Assessments, Parkinson's disease fatigue scale (PFS-16) and Parkinson's disease Questionnaire (PDQ-39).

Study Visits 1 to 9.

Visit 1 – Screening.

At the Screening Visit (Visit 1), study participants' information will be collected by study's delegated personnel for evaluation of trial eligibility. The following information is required to determine eligibility:

- Signing Informed Consent Form (prior to any trial-related activities).
- Collection of demographic information, such as age, race, ethnicity, date of birth, gender and relevant medical and surgical history.
- Collection of Medical History and concomitant medications, including relevant information about the past and present health of study participants.
- Inclusion and Exclusion criteria evaluation.
- Measurement of vital signs including respiratory rate, body temperature, blood pressure, pulse rate, oxygen saturation, weight and height.
- Collection of laboratory samples, including Comprehensive Metabolic Panel (CMP), Complete Blood Count (CBC), Coagulation Panel and Urine pregnancy test if female of childbearing potential.
- Physical examination by Principal Investigator, including clinical assessments such as MDS-Unified Parkinson's Disease Rating Scale and other assessments included in Table 3.
- Completion of neuro-quality of life questionnaire by study's participant and handwriting assessments.
- A video documenting study participant walking and standing from sitting will be recorded during this visit.

Within 28 days of the Visit 1 - Screening, the principal investigator must make a decision to determine participant's eligibility. Once, the eligibility of the subject has been confirmed by the principal investigator, the randomization process will be conducted.

Visit 2 – Infusion 1 (Baseline)

The following procedures are required during this visit:

- Reconfirm eligibility criteria.
- Update medical history and concomitant medications if any change occurred since last visit.

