Assessments Related to Endpoints

MDS-Unified Parkinson's Disease Rating Scale

The MDS-UPDRS scale refers to Movement Disorder Society - Unified Parkinson Disease Rating Scale, and it is a rating tool used to gauge the course of Parkinson's disease in patients. Each answer to the scale is evaluated by the principal investigator during the study visit. Some sections of the MDS-UPDRS scale require multiple grades assigned to each extremity.

Physical Examinations

A complete physical examination will be performed by the principal investigator or delegated sub-investigator, including general appearance, head, eyes, ear, nose, and throat (HEENT), neck, cardiovascular, thorax/lungs, abdomen, genitourinary, musculoskeletal, lymph nodes, skin,

neurological and mental status examination, height (at Screening only), and body weight at Visits 1, 2, 3, 4, 5, 6, 7, 8 and 9.

The principal investigator or delegated sub-investigator will evaluate the clinical significance of abnormal findings identified during physical examinations. Pre-existing conditions diagnosed through assessments and examinations at the screening visit or during the screening period are not adverse events but are recorded as medical history. If any clinically significant abnormal findings are discovered after informed consent or any pre-existing conditions worsen during the trial, these must be recorded as adverse events.

Vital Signs

Vital signs will be measured at Visits 1, 2, 3, 4, 5, 6, 7, 8 and 9 and will include respiratory rate, pulse rate, blood pressure (measured after the study participant has been in a seated position for more than 5 minutes of rest), body temperature and oxygen saturation. Clinical significance of any abnormal result must be evaluated by principal investigator. Clinically significant abnormal findings will be reported as adverse events.

Clinical Safety Laboratory Parameters

The following laboratory parameters should be collected at Visit 1, 2, 6 and 9.

- Comprehensive Metabolic Panel, also known as CMP or Chemistry Panel is a group of different tests that measure several substances in the study's participant blood.
- Complete Blood Count, also known as CBC, hemogram or CBC with Differential is a group of tests that evaluate the cells that circulate in blood, including red blood cells (RBCs), white blood cells (WBCs), and platelets.
- Coagulation Tests including Prothrombin Time (PT or PT-INR) to identify any coagulation disorder during study participation.

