- Urine Pregnancy Test, a urine sample, preferably collected during morning time, to confirm pregnancy during study participation. This test will be limited to Women of Childbearing Potential (WOCBP)

Other Assessments

Demography

Demographic data will be collected at the Screening Visit, including age, race, ethnicity, date of birth and gender.

Medical and Surgical History

Medical information on any previous concomitant illnesses, other than Parkinson's disease should be collected during Screening Visit and updated if needed during the following study

visits. For planned procedures/hospitalizations during the clinical trial, documentation should be completed at the time of the Screening.

Parkinson's disease and Previous Therapy for this disease

The date of diagnosis of Parkinson's disease, as well as previous treatments, will be recorded during Screening visit.

Concomitant Medication Review

Data concerning concomitant medications and procedures will be collected throughout the clinical trial. This data will be obtained at scheduled or unscheduled visits based on information provided by the patient.

Handling of Biological Samples

Sampling tubes, material for shipments of the samples and a laboratory manual detailing all sample collection and shipment procedures will be provided and distributed to the clinical trial site by the selected laboratory. Laboratory samples will be collected as per protocol during Visit 1 – Screening, and/or Visit 2 – Infusion 1 (Baseline), Visit 6 - Infusion 5 and Visit 9 – End of Study.

Adverse Events

Adverse Event

An *adverse event* (AE) is any symptom, sign, illness or experience that develops or worsens in severity during the course of the study. Intercurrent illnesses or injuries should be regarded as adverse events. Abnormal results of diagnostic procedures are considered as adverse events if the abnormality results in study withdrawal, a serious adverse event, leads to additional treatment or diagnostic tests, or is considered by the investigator to be of clinical significance. Information on all adverse events should be recorded immediately in the source documents, CRF and in the appropriate adverse event section of the source documents. All clearly related signs, symptoms, and abnormal diagnostic procedures results should be recorded in the source document and CRF, though should be grouped under one diagnosis.

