A clinical laboratory abnormality should be documented as an adverse event. Any adverse event that results in hospitalization or prolonged hospitalization should be documented and reported as a serious adverse event unless specifically instructed otherwise in this protocol. Any condition responsible for surgery should be documented as an adverse event if the condition meets the criteria for an adverse event. All unresolved adverse events should be followed by the investigator until the events are resolved, the subject is lost to follow-up, or the adverse event is otherwise explained

Serious Adverse Event

Adverse events are classified as serious or non-serious. A *serious adverse event* is any AE that is:

- fatal
- life-threatening
- requires or prolongs hospital stay
- results in persistent or significant disability or incapacity
- a congenital anomaly or birth defect
- an important medical event

Important medical events are those that may not be immediately life threatening but are clearly of major clinical significance. They may jeopardize the subject and may require intervention to prevent one of the other serious outcomes noted above. All adverse events that do not meet any of the criteria for serious should be regarded as *non-serious adverse events*. Serious adverse events that are still ongoing at the end of the study period must be followed up to determine the final outcome. Any serious adverse event that occurs after the study period and is considered possibly related to the study treatment or study participation should be recorded and reported immediately.

Adverse Event Reporting Period

The study period during which adverse events must be reported is normally defined as the period from the initiation of any study procedures to the end of the study treatment follow-up. For this study, the study treatment follow-up is defined as approximately 20 weeks following the last administration of study treatment.

Stopping Rules

Infusion Stopping Rules

Study treatment infusion will be stopped if a least one of the following events occur:

- 1. Allergic reaction as evidenced by severe dyspnea, bronchospasm, or hypoxia after the product has been administered intravenously.
- 2. Patient verbally decline the treatment at any moment prior, or during the infusion.
- 3. Hyperpyrexia develops after infusion administration begins (core body temperature greater than or equal to 104°F).

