8.1. Adverse Events Analyses

AEs will be coded using the most recent version of the Medical Dictionary for Regulatory Activities (MedDRA).

A treatment emergent adverse event (TEAE) is defined as an event that has onset date on the first day of exposure or after the first day of exposure to infusion treatment, and no later than 3 days after the last day of infusion treatment. AEs with missing start and/or stop dates will be assumed to be treatment emergent.

Treatment adverse events (TAE) are summarised descriptively, whereas non-TEAEs are presented in listings. TAE data will be displayed in terms of the number of subjects with at least one event (N), percentage of subjects with at least one event (%) and the number of events E.

Summaries of TAE and of serious AEs will be presented as an overview, including all AEs, AEs listed by severity, serious AEs, AEs by relation to treatment, action taken after AEs occurred and treatment advised, and the outcome of AEs.

Furthermore, summary tables based on system organ class and preferred terms are made for:

- All TAEs
- Serious AEs
- AEs leading to withdrawal of study

Individual adverse events will be listed.

The details of the planned displays are in Error! Reference source not found..

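### A pre-existing condition first found at screening fits two conflicting recording rules, and the SAP's missing-date rule can then count it as treatment emergent

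*Protocol*

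**What the plan says.** **Protocol, Physical Examinations.** Two consecutive sentences apply. The first: "Pre-existing conditions diagnosed through assessments and examinations at the screening visit or during the screening period are not adverse events"; they go into medical history. The second opens "If any clinically significant abnormal findings are discovered after informed consent" and makes AE recording mandatory for such findings, and likewise for any earlier condition that gets worse in the course of the trial.

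**Protocol, Visit 1 – Screening.** The list of procedures opens with "Signing Informed Consent Form (prior to any trial-related activities"). It contains no AE assessment.

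**Protocol, Adverse Event.** An AE is "any symptom, sign, illness or experience that develops or worsens in severity during the course of the study". The same section also makes an abnormal diagnostic result an AE if the investigator considers it clinically significant, and asks for laboratory abnormalities to be documented as AEs.

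**Protocol, Vital Signs.** Measurement covers Visits 1 to 9. Clinically significant abnormalities are reported as AEs, with no exception for screening.

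**Protocol, Adverse Event Reporting Period.** Reporting normally covers "the period from the initiation of any study procedures to the end of the study treatment follow-up". In Table 3 the AE/SAE row has eight marks for nine visits, laid out from Visit 2 onwards.

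**SAP 8.1.** A TEAE needs an onset on or after the first day of exposure (an upper time limit also applies, but is not at issue here). The section then adds: "AEs with missing start and/or stop dates will be assumed to be treatment emergent".

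TEAEs appear under Primary Endpoints in the protocol and alongside the primary objective in the SAP's table of objectives and endpoints.

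**The concern.** The second Physical Examinations sentence turns on when a finding is discovered, not on when it arose. A condition of long standing that comes to light at the screening examination is discovered after consent, so two careful members of staff could file it differently and both be following the text.

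Alone, that would be a recording ambiguity. It reaches a primary endpoint through SAP 8.1, where a missing date overrides the onset criterion. No sentence exempts an event already observed before the first infusion. A condition that cannot be an effect of treatment could then appear in the TEAE summaries, and whether it does would depend on which sentence the site followed and which date field was left blank.

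**Working it through.** The documents state no TEAE rate or calculation for this point, so there is no figure to reproduce. The check is mainly a comparison of the rules.

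**Step 1. Which screening findings meet both sentences?**

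| Finding | Pre-existing-condition sentence | After-consent sentence | Result |
|---|---|---|---|
| Known before consent, not worsening | Medical history | Not triggered | History only |
| Pre-existing, first detected at screening, not clinically significant | Medical history | Not triggered | History only |
| Pre-existing, first detected at screening, clinically significant | Medical history | AE | **Both** |
| New illness between consent and first infusion | Not covered | AE if clinically significant | No conflict |

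The overlap is the third row only.

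**Step 2. Does other text settle the third row?** The AE definition favours medical history, because the condition neither developed nor worsened during the study. The absence of a Visit 1 mark in Table 3 fits that reading. The vital-signs rule, the diagnostic and laboratory abnormality rules and the start of the reporting period point to AE. No order of precedence is given.

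**Step 3. What does SAP 8.1 do with a finding recorded as an AE before the first infusion?**

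| Start date | Stop date | Onset criterion | Missing-date sentence | Result |
|---|---|---|---|---|
| Known, pre-dose | Known | Not a TEAE | Not triggered | Not a TEAE |
| Missing | Known or missing | Cannot be applied | TEAE | **Counted** |
| Known, pre-dose | Missing (for example, ongoing) | Not a TEAE | TEAE | **Contradiction** |

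The last row assumes that an ongoing condition has a blank stop date, which is the literal reading. SAP 10.1.2, on missing data, does not address AE dates.

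**Step 4. Scale.**

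- *One participant.* The protocol randomises 12 per arm. If the affected participant has no other TEAE, the arm's incidence moves by 1/12 = 8.3 percentage points. Across all 24 it moves by 1/24 = 4.2 points. SAP 8.1 also reports the number of events, which rises by one for each such record in any case.
- *Several participants.* Let q be the probability that a dosed participant has at least one such record. The documents do not give q; 2% to 20% is an assumption to show the range. The expected number is 24q, and the chance of at least one among n participants is 1 − (1 − q)^n.
- *Dilution.* If q is equal in both arms and independent of true TEAEs, observed incidence is 1 − (1 − p)(1 − q), where p is the true incidence. The difference between arms is then multiplied by (1 − q).

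| Assumed q | Expected among 24 | At least one among 24 | At least one in an arm of 12 | Difference multiplied by |
|---|---|---|---|---|
| 2% | 0.5 | 38% | 22% | 0.98 |
| 5% | 1.2 | 71% | 46% | 0.95 |
| 10% | 2.4 | 92% | 72% | 0.90 |
| 20% | 4.8 | 99.5% | 93% | 0.80 |

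Within this range dilution is modest. The more practical issue is that one or two such records are visible in a table with 12 per arm.

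**The case against.** The best defence is that the protocol can be read coherently. The AE definition requires something to develop or worsen during the study. The first Physical Examinations sentence is a specific rule for pre-existing conditions, and the second can be taken to cover everything else. Table 3 fits this, and a reporting period that starts with the first procedure may be meant only for new events during screening. That reading is sensible and probably intended. It is not what the second sentence says, and the vital-signs, diagnostic and laboratory rules carry no screening exception. The defence also does nothing for SAP 8.1, whose missing-date sentence is wrong for any event already seen before dosing.

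Other parts of the defence stand and limit the point:

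- The route is conditional: the site must choose the AE reading, a date must be missing, and the participant must later be dosed. Screen failures are outside the Safety analysis set (SAP section 4).
- Exclusion criteria 5, 8 and 9 remove many participants with significant conditions or screening laboratory abnormalities. Physical examination and vital signs are therefore the main sources.
- SAP 8.1 summarises these events descriptively, names no test for them, and lists individual AEs, so a reader could trace an odd entry.

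A reader might go further and infer that every screening finding is caught, that onset dates would usually be unknown, or that the TEAE comparison would be heavily diluted. The documents support none of these. The overlap is one class of finding, medical history is taken at Visit 1, nothing says whether sites enter the discovery date as onset, and no rate is given.

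**Conclusion.** The point holds in a limited form. The protocol gives two incompatible instructions for a clinically significant pre-existing condition first detected at screening. SAP 8.1 contains a rule that gives a wrong answer when such a finding is recorded as an AE with a missing date. Read literally, that includes an ongoing condition with a known pre-dose start and no stop date.

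The size is 8.3 percentage points of an arm's TEAE incidence for each affected participant with no other TEAE. How many there would be cannot be learned from the documents.

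A reader might also infer bias towards one arm. That is not supported: screening precedes randomisation, assessors are blinded, and the rule is the same for both arms. The expected effect is inflation in both arms with some dilution, though chance imbalance is possible with 12 per arm. The point is worth correcting because the endpoint is primary and the correction is cheap, not because a large distortion has been shown.

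**What to change.** 1. **SAP 8.1.** State that an event with a known onset before the first infusion, or first observed before it, is not treatment emergent whatever date is missing, unless it worsens after the first infusion. Assume treatment emergence only when the available information cannot place the event before the first infusion. A missing stop date alone should not make an event treatment emergent.
2. **Protocol, Physical Examinations.** Limit the second sentence to findings that are new or worsened since informed consent. Pre-existing conditions first detected at screening then stay medical history. New illness, injury or procedure-related events between consent and first infusion stay pre-treatment AEs. Put the same limit on the vital-signs rule and on the diagnostic and laboratory abnormality rules in the Adverse Event section. Classing everything before the first infusion as medical history would be simpler, but it would contradict the protocol's own treatment of intercurrent illness and its reporting period.
3. **Protocol, Table 3.** Reconcile the AE/SAE row with the Adverse Event Reporting Period.

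The cost is a short SAP revision, plus a protocol amendment covering three sections and one table row; no new data or participants are needed. The SAP change alone protects the TEAE count, and it is the part that matters most if screening is already complete.
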